## PROTOCOL

### A Cognitive Behavioral Therapy Intervention (FREE) to Reduce Fear of Hypoglycemia in Young Adults with Type 1 Diabetes

#### 1. ABSTRACT

In persons with type 1 diabetes (T1DM), iatrogenic hypoglycemia is the major limiting factor in achieving optimal blood glucose control. All persons with T1DM are at risk for hypoglycemia (blood glucose level < 70 mg/dl), which is life-threatening and has serious physical symptoms and psychological sequelae that lead to profound fear of future hypoglycemic events. This fear results in greater glucose variability (the intra-day fluctuations in blood glucose), due to under- or overcompensation of food intake, insulin dosing, or physical activity, as well as anxiety, depression, and reduced quality of life. Greater glycemic variability (GV) is associated with a higher risk of hypoglycemia and diabetes complications. Young adults are particularly at risk because they report greater FOH and have poorer glycemic control. A major gap exists in how to manage FOH as a crucial component of diabetes self-care. Our overall objective is to reduce FOH and improve diabetes self-management, glycemic control, and variability in young adults with T1DM. We specifically aim to: (1) Determine the feasibility of an 8-week CBT-based intervention to reduce FOH and (2) obtain means and standard deviations of group differences from baseline to program completion on the outcomes of FOH, self-management, glycemic control and glycemic variability in young adults with T1DM who experience FOH. To achieve these aims, we propose a randomized control pilot trial in 10 young adults aged 18 to 30 years with T1DM. Participants will be screened for FOH levels. Eligible subjects will be randomized to the intervention (Fear Reduction Efficacy Evaluation [FREE]) program or attention control group. A 1-week run-in phase is planned, with baseline measures of FOH and 24-hour real-time continuous glucose monitoring recordings (RT-CGM) to calculate GV for both groups. The intervention group will participate in eight weekly one-hour sessions using a cognitive behavioral therapy (CBT) and exposure treatment for specific fears. RT-CGM and a daily FOH diary will be used as feedback cues. The control group will wear a 24-hour RT-CGM device during the same 8-week period and return for weekly RT-CGM site changes by study staff. At completion, FOH will be measured, and RT-CGM recordings will be analyzed to determine within-group and between-group differences. The findings from this proposed study will serve as the foundation for a larger clinical trial to reduce FOH and improve self-management, glycemic control, and variability. Meeting these goals will have important clinical implications to reduce diabetes complications and improve quality of life in young adults with T1DM.

#### 2. RESEARCH PLAN

##### B. Specific Aims

**The specific aims of this IRSP pilot study are:**

1. Determine the feasibility of the 8-week fear reduction intervention FREE in young adults with T1DM who report FOH. Feasibility will be determined through analysis of recruitment, retention, and participant evaluation.
2. Obtain means and standard deviations of within-group and between-group differences from baseline to program completion (8th week) and post-program (12th week) on the outcomes of FOH, self-management, glycemic control (A1C), and GV. This data will be used for calculation of effect sizes for a future larger study.

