## 3. Approach

### 3.1. Preliminary Studies

**3.1a. Research Team Expertise.** This application brings together an interdisciplinary team with shared (T1DM, FOH, CGM technology for GV measurement, chronic illness, clinical practice) and complementary (CBT, feedback, intervention studies, clinical diabetes education [CDE]) expertise. Collectively, the team's research strengths span conceptual, methodological, clinical, statistical, and research abilities in the areas of self-management and chronic disease.

**3.1b. Preliminary Findings.** We successfully conducted a study using a prospective repeated measures design, using CGM and a daily fear diary in 30 young adults with T1DM. FOH was linked to GV. (1) Significant temporal relationships emerged in which same-day fear levels were associated with same-day GV ( $r = .232, p = < .05$ ), and previous-day fear levels were associated with next-day GV ( $r = .205, p < .05$ ). This between-day relationship was stronger for those who experienced four or more hypoglycemic episodes per week ( $r = .483, p < .01$ ). (2) FOH was reported by 78% of the sample. (3) During the 6-day CGM recording period, 27% were identified as hyper-responders, indicating that they reported and treated more presumed hypoglycemic episodes (based on daily diary entries) than actual biochemical hypoglycemic episodes measured through CGM recordings. (4) Optimal glycemic control (A1C < 7%) was not consistently associated with low GV. Our data demonstrated that nearly half (45%) of the sample had A1C levels at or below 7.0, yet 57% of those with optimal A1C levels had high GV ( $> 52$  dl glucose standard deviation).

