### 3.2. Design and Methods

**3.2a. Overview.** Following a 1-week run-in phase, ten young adults aged 18 to 30 years with T1DM ( $\geq 1$  year) and who experience FOH will be randomized to an intervention or attention control group. The intervention group will participate in eight weekly one-hour sessions using a CBT-based approach (FREE), wear a RT-CGM device, and keep a daily diary. The attention control group will also wear a RT-CGM device for 8 weeks but will not participate in weekly sessions and will not keep a diary. Data will be collected: (1) at the beginning of a 1-week run-in period (week 0); (2) at completion of the intervention at the end of 8 weeks (week 8); and (3) post-program at 12 weeks. At completion, FOH, self-management, and A1C will be measured and RT-CGM recordings will be analyzed to determine within-group and between-group differences.

**3.2b. Setting and Sample.** The study intervention will take place at the University of Illinois at Chicago (UIC) Medical Center and College of Nursing. Inclusion criteria: (1) 18-30 years old, (2) diagnosed with T1DM  $\geq 1$  year and receive medical care from an endocrinologist, (3) use insulin pump therapy, and (4) have self-reported FOH (screening questionnaire). Exclusionary criteria: (1) pregnant or breastfeeding, (2) actively treated for a mental health condition, (3) have a co-existing chronic illness or taking medications (excluding insulin) that may influence diabetes self-management or GV.

**3.2c. Recruitment.** Subjects will be recruited through Chicago metropolitan area university medical centers, local diabetes websites, and organizations using flyers, e-announcements, and recruitment letters. At UIC, we will identify potentially eligible subjects through the electronic medical record system and send recruitment letters. The University of Illinois clinics saw over 900 patients with T1DM; thus, there is a sufficient pool from which to recruit. We have been successful in recruiting using these methods for our previous studies.

**3.2d. Sample Size Determination.** The sample size of 10 subjects ( $n = 5$  intervention group; 5 intention control group) will be sufficient to test the feasibility of the study protocol and to obtain preliminary outcome measures.

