### 3.2g. Data Analysis

1. The feasibility of the program will be evaluated by assessment of recruitment, retention, and participant evaluation. Itemized logs of recruitment sites, methods, responses, eligible subjects, and consented subjects will be documented. Retention will be evaluated through documentation of weekly attendance and compliance with RT-CGM site changes. As part of the feasibility assessment, we will also track the number of RT-CGM sensor failures, RT-CGM placement sites, time to failure, and any adverse sensor site problems. Acceptability will be determined through participant evaluation (Appendix C).

2.) We will calculate means and standard deviations of within-group and between-group differences from baseline to program completion (8th week) and post-program (12th week) on the outcomes of FOH, self-management, glycemic control (A1C), and GV.

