### 3.2h. Timeline

Year 1	Mar	Apr	May	June	July	Aug	Sept	Oct	Nov	Dec	Jan	Feb	Mar	Total
Study set up	X	X	X											
FREE subjects				2		2			1					5
Control subjects				2		2			1					5
Total subjects				4		4			2					10

**3.2j. Pilot study limitations.** One of the limitations is that the small convenience sample may not be representative of the population. This limitation is offset by the fact that this is strictly a feasibility pilot to inform and strengthen a larger study in terms of recruitment, retention and acceptability.

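### Aim 2 uses 5-versus-5 data to calculate effect sizes for a larger study, but plans no interval and sets no limit on how those imprecise estimates are used

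*Combined protocol and SAP*

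**What the plan says.** Section B, Aim 2, is to obtain means and SDs of within-group and between-group differences at weeks 8 and 12 for fear of hypoglycemia (FOH), self-management, A1C and glycemic variability (GV). It then gives the purpose: "This data will be used for calculation of effect sizes for a future larger study".

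Section 3.2d fixes the size without a calculation. It begins "The sample size of 10 subjects", splits them equally ("intervention group; 5 intention control group"), and says that this number "will be sufficient to test the feasibility of the study protocol and to obtain preliminary outcome measures".

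The whole outcome analysis is item 2 of section 3.2g: "We will calculate means and standard deviations of within-group and between-group differences from baseline" to weeks 8 and 12. It mentions no confidence interval, and it does not say which SD would standardise an effect size.

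Section 3.2j names the small convenience sample as a limitation, but only for representativeness. It adds that "this is strictly a feasibility pilot to inform and strengthen a larger study in terms of recruitment, retention and acceptability". Effect sizes are not on that list.

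Section 3.1b describes the team's earlier study, "using CGM and a daily fear diary in 30 young adults with T1DM". No section links it to sizing the larger study, and no section gives a clinically important difference.

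**The concern.** Aim 2 gives the outcome data a job beyond description: they are to feed the planning of a larger study. With 5 per arm, both parts of an effect size, the mean difference and the SD, are very imprecise. The plan does not arrange to show that imprecision, and it puts no limit on how the estimates are used.

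The next study is what is at stake. A planning effect that is too large by chance gives a study that is too small. One that is too small by chance gives a study that is needlessly large, and an effect at or below zero gives no size at all. The conduct of this pilot and its feasibility aim are untouched.

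**Working it through.** **Inputs from the protocol.** 5 per arm (3.2d, matching the 5 + 5 = 10 in the 3.2h timeline); means and SDs of change as the planned summaries (3.2g item 2). The protocol has no sample-size calculation to reproduce: it states no alpha, power, effect or SD.

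**Assumptions.** Normal data, equal SDs in the two arms, all 5 per arm complete. True effects are illustrative, because the protocol gives none.

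**1. Between-group difference in change, 95% CI half-width in pooled SDs.** Formula: t(0.975, df) × √(1/n₁ + 1/n₂).
- 5 v 5, 8 df: 2.306 × √(2/5) = 1.46.
- 4 v 4 (one dropout per arm), 6 df: 2.447 × √(2/4) = 1.73.

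**2. Pooled SD.** 95% limits as multiples of the estimate: √(df / chi-square quantile). With 8 df: √(8/17.53) = 0.68 and √(8/2.18) = 1.92.

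**3. Within one arm (n = 5, 4 df).** Half-width of the mean change: 2.776/√5 = 1.24 SDs. SD limits: 0.60 to 2.87 times the estimate.

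**4. An observed standardised difference (d) of 0.5.** Inverting the noncentral t distribution, with t = d × √2.5:

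| Completers | 95% CI for d |
|---|---|
| 5 v 5 | −0.78 to 1.75 |
| 4 v 4 | −0.93 to 1.89 |

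**5. Chance of an observed effect at or below zero.** With true effect δ, this is Φ(−δ × √2.5).

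| Assumed true δ | Φ argument | Probability |
|---|---|---|
| 0.3 | −0.47 | 32% |
| 0.5 | −0.79 | 21% |
| 0.8 | −1.26 | 10% |

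**6. Price of allowing for uncertainty in the SD, by one convention.** The one-sided 80% upper limit on 8 df is √(8/chi-square(0.20, 8)) = 1.32 times the estimate. Take a target difference of half the pilot SD, two-sided alpha 0.05 and 80% power. The t-test formula gives 63.8, so 64 per arm, with the raw SD. With the upper limit, d = 0.5/1.32 = 0.379, which gives 110.3, so 111 per arm.

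**7. Whether the data exist for each planned estimate.** Aim 2 and 3.2g item 2 ask for week-12 differences in all four outcomes, GV included. Section 3.2f3 describes glucose monitoring only during the run-in and the 8-week intervention. Table 1's layout is broken in the text available, so it does not settle the matter. A week-12 GV change may have no data behind it.

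**The case against.** The strongest reply is that the protocol promises little. Section 3.2d claims only preliminary measures, 3.2j calls the study strictly a feasibility pilot, and no test or efficacy claim is planned. That stands as a defence of the sample of 10 and of the feasibility aim. It does not cover the last sentence of Aim 2, which gives the outcome data a planning use that 3.2j does not list.

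A reader might infer that the next study will be sized directly on the observed pilot effect, so that chance would set its size. The documents do not support this. They say effect sizes will be calculated for a larger study, but they give no sizing rule and do not exclude other inputs. The 21% in step 5 describes the estimate, not a planning decision the team has announced.

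A reader might also infer that the imprecision would be hidden. That goes too far: published means, SDs of change and group sizes would let anyone compute a t-based interval. What remains is that the plan neither reports the interval nor says how the estimate may be used.

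It can fairly be said that a later protocol should settle its own sizing method. Even so, this protocol states the intended use and can qualify it in a sentence. No single convention for the SD needs to be prescribed.

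Finally, the earlier study of 30 might seem to supply the missing precision. As described in 3.1b it had one 6-day recording period, so it gives no SD of 8-week change. Nor was it limited to people with FOH: 78% reported it.

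**Conclusion.** The point holds as a cheap improvement, not as a flaw in the pilot's size or conduct. The 5-versus-5 data are committed to effect-size calculation for a larger study, with no planned interval, no other sizing basis named and no statement of imprecision. The precision is ±1.46 pooled SDs for a between-group difference and 0.68 to 1.92 times the estimate for the pooled SD. These figures assume normal data, equal SDs and no dropout; one dropout per arm widens the first to ±1.73. The 21% also assumes a true effect of 0.5, and the figure runs from 32% to 10% over true effects of 0.3 to 0.8. Confidence is high on the arithmetic and on the missing interval. How the team would in fact use the estimates is not stated.

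**What to change.** 1. **Section 3.2g item 2.** Add: *Between-group differences in change will be reported with 95% CIs, both in raw units and as Hedges' g (standardised by the pooled within-group SD of change). Within-group mean changes will be reported with 95% CIs. All are descriptive.* Limit this to outcomes and times at which data are collected, and reconcile week-12 GV between Aim 2, 3.2g and 3.2f3.
2. **Aim 2, last sentence.** Replace with: *The larger study will be sized on a clinically important between-group difference chosen in advance for its primary outcome, not on the observed pilot effect alone. The pilot SD will be used only with its uncertainty allowed for, for example through an upper confidence limit or external SDs of the same quantity.* The choice of convention can stay with the team.
3. **Section 3.2d or 3.2j.** Add: *With 5 completers per group, a between-group difference in change is estimated to within ±1.46 pooled SDs (95% CI), and the pooled SD to within 0.68 to 1.92 times its estimate.*

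**Cost.** A few sentences in three places, with no extra participants. The intervals come from summaries already planned. The team must later choose a primary outcome and an important difference, which the protocol does not give. A conservative SD also enlarges the next study: in the step 6 example, about 111 rather than 64 per arm.

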##### C. Research Strategy

###### 1. Significance

**Why focus on FOH in young adults?** Despite refinements in insulin therapy and advancements in glucose-sensing technology over the past several decades, fear of hypoglycemia (FOH) remains a critical deterrent to T1DM self-management, psychological well-being, and quality of life (QOL). Fear is conceptualized as an emotion arising from a cognitive appraisal of a specific threat or danger. Normal fear is adaptive, stimulating more vigilance and improved performance; whereas heightened fear leads to increased anxiety and may result in a delay to action or inappropriate action. Anxiety may mimic the symptoms of [name] CBT Fear Reduction Program Protocol, Version 3, 4-29-16

hypoglycemia and impair its detection, further complicating the problem. At the extreme, fears can develop into anxiety disorders and phobias. Young adults experience higher FOH levels than adolescents and middle-aged adults; thus, it is critical to develop strategies to assist young adults in coping with FOH. Previous negative experiences of hypoglycemia influence health behaviors used in diabetes self-management, including insulin dosing, dietary patterns, and physical activity. Insulin doses may be inappropriately reduced in anticipation of hypoglycemia, and diet may be modified to avoid hypoglycemia. Dietary modifications may include excessive eating, particularly more carbohydrates or snacking at night. These excessive modifications lead to increased GV.

Over the past three decades, a number of newer technologies have been designed to help patients with diabetes manage their treatment regimens, including continuous glucose monitoring (CGM) systems, insulin pumps, sensor-augmented pump therapy with threshold suspend features, and insulin bolus calculators. While these devices have improved glucose control (i.e., A1C), improved glucose control has not consistently translated into reduced FOH.

**What has been used to address FOH?** Diabetes education programs typically discuss FOH but have not developed strategies to manage it. Education, motivational interviewing, and cognitive behavioral therapy (CBT) interventions have been developed to improve glucose control, but no program has been established to specifically address FOH. Improved glucose management has had variable effects on FOH. Outcomes have demonstrated that, as glucose levels are lowered, worry levels have not consistently decreased, and any improvements that have occurred have not been sustainable. We hypothesize that the lack of consistent and sustainable reductions in FOH has occurred because the focus of these programs has been on glycemic control, not on FOH. Any strategy that focuses on managing glucose to near-normal levels must include methods to cope with the fear that lower blood glucose levels could lead to hypoglycemia. FOH management must be a part of diabetes care. *A fear reduction program, informed by the proposed study, may provide a more comprehensive approach to diabetes care that reduces anxiety and improves glycemic control and variability.*

**Why is glycemic variability (GV) important?** Lower hemoglobin A1C levels are associated with a reduction in microvascular complications. Although A1C provides a biomarker for average blood glucose over a 2- to 3-month period, it does not capture daily blood glucose level fluctuations that occur. Evidence supports the role that GV (daily fluctuation) plays in the generation of oxidative stress, endothelial dysfunction, and diabetes complications in T1DM. High degrees of GV are associated with more frequent episodes of hypoglycemia and fluctuations between glucose extremes (i.e., hypo- to hyperglycemic levels), which may occur with overtreatment of a hypoglycemic episode. *GV is directly influenced by self-management behavior and is amenable to change with appropriate intervention.*

**Why use a cognitive behavioral approach (FREE) to reduce FOH?** Increased FOH creates anxiety, which may impair awareness of internal and external blood glucose cues and leave individuals less prepared to take action. Heightened fear may develop due to previous negative hypoglycemic thoughts, feelings, and experiences that create a conditioned negative response to future fear triggers. An approach that uses cognitive behavioral techniques such as cognitive restructuring, exposure to feared stimuli, and regular monitoring of symptoms has been effective in other populations. In the proposed study, the FREE program will incorporate CBT to reframe the fear experience and reduce the adverse emotional response. Exposure therapy will be used to reduce anxiety through habituation to previously anxiety-provoking situations. Feedback using RT-CGM readings and review of a fear diary will be used as cues to reinforce learning. The goal is not to replace standard diabetes therapy, but improve diabetes self-management through fear reduction. Our premise is that negative thoughts, feelings, or experiences of hypoglycemia increase FOH. This compromises diabetes self-management and increases GV. Our program is designed to reduce FOH and improve diabetes self-management, which will lead to improved glycemic control and variability. (Figure 1).

[figure not shown]

Figure 1. Components of FREE program

## 2. Innovation

With most diabetes self-management research focused on blood glucose management, a FOH reduction intervention represents a novel approach to addressing the role of hypoglycemic fear in glycemic control and variability. Most individuals with T1DM struggle with hypo- and hyperglycemia and develop a profound fear from these experiences. FOH does not resolve with education alone, and the magnitude of the problem is poorly understood, as well as greatly under-appreciated. As the incidence of T1DM increases worldwide, the scope of the problem will only rise. To our knowledge, we are the first to identify the temporal relationships between FOH and GV (see 3.1b). These findings provide strong justification for an intervention that specifically targets FOH. In this R21, our team proposes to pilot test a CBT and exposure-based therapy intervention that is unique to diabetes care but has been effective in reducing fear and anxiety in other populations with chronic illness. This methodology will provide feedback on progress toward FOH reduction and GV through weekly diary and RT-CGM analysis. We focus on young adults because they have reported higher FOH levels than older adults and young children and they are becoming responsible for their diabetes management in new and challenging roles and situations. Improvement in diabetes self-management in this age group could facilitate the prevention or delay of diabetes complications later in life.

## 3. Approach

### 3.1. Preliminary Studies

**3.1a. Research Team Expertise.** This application brings together an interdisciplinary team with shared (T1DM, FOH, CGM technology for GV measurement, chronic illness, clinical practice) and complementary (CBT, feedback, intervention studies, clinical diabetes education [CDE]) expertise. Collectively, the team's research strengths span conceptual, methodological, clinical, statistical, and research abilities in the areas of self-management and chronic disease.

**3.1b. Preliminary Findings.** We successfully conducted a study using a prospective repeated measures design, using CGM and a daily fear diary in 30 young adults with T1DM. FOH was linked to GV. (1) Significant temporal relationships emerged in which same-day fear levels were associated with same-day GV ( $r = .232, p = < .05$ ), and previous-day fear levels were associated with next-day GV ( $r = .205, p < .05$ ). This between-day relationship was stronger for those who experienced four or more hypoglycemic episodes per week ( $r = .483, p < .01$ ). (2) FOH was reported by 78% of the sample. (3) During the 6-day CGM recording period, 27% were identified as hyper-responders, indicating that they reported and treated more presumed hypoglycemic episodes (based on daily diary entries) than actual biochemical hypoglycemic episodes measured through CGM recordings. (4) Optimal glycemic control (A1C < 7%) was not consistently associated with low GV. Our data demonstrated that nearly half (45%) of the sample had A1C levels at or below 7.0, yet 57% of those with optimal A1C levels had high GV ( $> 52$  dl glucose standard deviation).

